
Specific Aims

1. To determine the effects of Diet+BPA, compared to Diet+No BPA on muscle insulin sensitivity (assessed by euglycemic hyperinsulinemic clamp technique and glucose stable isotope infusion) and insulin-stimulated hepatic glucose suppression.
2. To determine the effects of Diet+BPA, compared to Diet+No BPA, on fasting hormones (C-peptide, Pro-insulin), inflammatory markers (adiponectin), and sex hormones (17-beta-estradiol), linked to the progression to type 2 diabetes.

Exploratory Aim will examine fecal microbiome species diversity and communities in participants randomized to Diet+BPA compared to Diet+No BPA.

APPROACH

Preliminary Studies. The investigative team on this proposal has several prior collaboration and complementary expertise in pathophysiology of type 2 diabetes (Drs. [name], [name], [name], [name], [name]), experimental feeding and assessment studies (Drs. [name], [name], [name]), energy intake and expenditure controlled studies (Drs. [name], [name], [name]), assessment of insulin sensitivity and hepatic glucose suppression (Drs. [name], [name], [name]), assessment of endocrine disruptors (Drs. [name], [name]), and statistical methods of randomized controlled designs (Drs. [name], [name], [name], [name]).

Oral BPA Consumption in Adults. The PI ([name]) and Co-I's ([name] and [name]) recently completed the first human study to our knowledge examining the effect of a single, oral dose of BPA on

[figure not shown]

Figure 1. Plasma geometric mean glucose concentrations (A), insulin concentrations (B), and C-Peptide concentrations (C).

* BPA 50 significantly different than PL ($P<0.05$)
 **BPA 50 significantly different than BPA 4 ($P<0.05$)
 PL, Placebo; BPA 4, bisphenol A 4 μ g/kg BW; BPA 50, bisphenol A 50 μ g/kg BW

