3-weeks, a significant treatment x time ($P<0.02$) effect on creatinine-corrected urinary BPS concentrations was observed such that BPS decreased by 1.27 μ g/g creatinine in the intervention group and decreased slightly by 0.09 μ g/g creatinine in the control group. There were no significant changes in BPA concentrations ($P>0.05$).

METHODS

Overview This experimental study is a 2-group randomized, clinical trial comparing a 4-day energy balance diet plus oral BPA consumption at 50 μ g/kg body weight (Diet+BPA) vs. 4-day energy balance diet plus oral placebo consumption (Diet+No BPA). Forty participants will be randomized to Diet+BPA and Diet+No BPA and will reside in a supervised environment at Cal Poly's sleep research facilities in the College of Liberal Arts under the supervision of [name] for 6 days (2-day baseline run-in, followed by 4-day treatment). Main outcome measures (muscle insulin sensitivity and hepatic glucose suppression) will be assessed at baseline and treatment periods.

Experimental Protocol

Participants Forty, 18 to 50 years old, non-dieting, sedentary (≤ 3 hour/week of aerobic exercise), normal-weight (BMI = 18.5 to 24.9 kg/m²) participants will be recruited. All participants will be healthy, weight-stable for the previous 6 months, free of any metabolic or chronic disease, non-smoking, and sedentary, assessed by

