Health and Fitness History and Physical Activity Readiness (PAR-Q) questionnaires. We chose normal-weight participants to minimize the potential confound of high BPA exposure and insulin resistance as it relates to obesity.^{8,23-25} Both men and women will be included in the study, as previous reports have shown that total BPA exposure may not differ by sex.²⁶ A fasting hemoglobin A1C blood draw will be conducted by a certified phlebotomist and assessed at Central Coast Pathology, as done in our previous studies. **Exclusion criteria include:** Hemoglobin A1C based on the American Diabetes Association guidelines of 5.7 to 6.4% (Prediabetes) or >6.4% (Diabetes), any metabolic or chronic disease, including impaired glucose tolerance or type 1 or type 2 diabetes, colitis or any inflammatory bowel condition, neurologic or psychiatric conditions, smoking, unsafe dieting practices, special diets (e.g. vegetarian, low-carbohydrate, Paleolithic, etc.) assessed by a Health History questionnaire, and pregnant women or women trying to become pregnant. All women will be given a pregnancy test (First Response, Princeton, NJ) that detects urine human chorionic gonadotropin prior to their participation. All testing in women will occur in the early follicular phase (1 to 4 days after start of menstruation) of the menstrual cycle. San Luis Obispo county has approximately 30-40% Hispanic adults, 55-65% non-Hispanic white, 5% non-Hispanic African-American, and 1% non-Hispanic Asian. All race/ethnicities will be eligible for this study with a target enrollment of 20% Hispanic and 80% non-Hispanic. We have previously successfully recruited this racial/ethnic target.²⁷ Because all participants will undergo a 2-day baseline run-in with a diet low in BPA, which has been shown to reduce BPA by 66%,²⁸ background BPA exposure is not an exclusion.

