Recruitment Our previous BPA consumption, and other feeding and exercise trials showed that recruitment of normal-weight, sedentary participants are extremely feasible with limited participants lost to follow-up (>98% retention).²⁹⁻³³ In the current study, we anticipate similarly high retention. We will employ comparable retention procedures, including financial incentives (\$500 total) for completing all visits. The breakdown of participant payment is: Baseline testing = \$100, Treatment days = \$400. During the treatment phase for 4 days participants will have a safety blood draw (see below for more detail) to assess liver, kidney and immune function at the Cal Poly Health Center. Cal Poly students will be charged \$7.50 per draw (total \$30). However, treatment days compensation will be increased to \$430 to cover these costs if the participant is a Cal Poly student.

BPA Dose and Duration The dose of BPA selected in the proposed study is consistent with the US EPA reference dose of 50 µg/kg body weight. The National Toxicology Program reported that that typical BPA exposures range from 0.43 to 1.5 µg/kg body weight.³⁴ Based on occupation work, BPA exposure can be as high as 100 µg/kg body weight however.³⁴ The BPA dose selected is well below the FDA **no-observed-adverse-effect level** of 5 mg/kg BW per day.³⁵ The pharmacokinetics of 50-100 µg/kg BW of BPA has a blood concentration max occurring at ~1 hour after consumption, 92% of BPA is present in urine at 24 hours, and urinary half-life of 4-5.5 hours, with no reported side effects.³⁶⁻³⁸ Our preliminary oral BPA consumption protocol at 4 µg/kg BW and 50 µg/kg BW had no gastrointestinal distress or subjective appetite changes. Thus, we anticipate no long-term negative effects of BPA consumption at 50 µg/kg BW as this is the reference dose in humans per the US EPA. Nevertheless, we will have medical supervision by [name] (Board certified internist at the Cal Poly Health Center), throughout the entire study and will assess four hepatic function tests, one at baseline and three during treatment on days 4-6. Also, after completion of the study, all subjects will be offered a 2-day “fresh food” diet that has been shown to reduce BPA exposure by 66%,²⁸ or will be provided with a \$50 gift card to a natural food market (participant will choose). In our previous BPA consumption study, we successfully used a similar protocol to limit BPA exposure after completion of the study.

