Diet, Activity and Sleep Monitoring and Control

[figure not shown]
Participants will reside in our laboratory facilities in the College of Liberal Arts sleep facility for a total of 6 days (2-day baseline run-in followed by 4-day treatment) during which energy intake, energy expenditure, and sleep will be closely monitored and controlled.³⁹ Maintaining and controlling energy balance is necessary to isolate whether BPA has an effect on muscle insulin sensitivity and hepatic glucose suppression independent of changes in weight. Participants will be provided all food, will wear an Actigraph GT3X accelerometer on their non-dominant wrist for the entire 6 days, and ActiPal on their dominant leg (to assess sitting and standing), and perform no physical activity beyond daily living.⁴⁰ Participants will be allowed to leave our facilities and attend school or work but will be required to wear the Actigraph and ActiPal to ensure their typical low activity levels. Participants will consume all foods at our facilities and must return each night by dinnertime to sleep in our facilities. Participants in both conditions will be provided an energy balance diet low in bisphenols for all 6 days

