participant to lay flat on their back without moving for approximately 10 minutes. Cell mutation can occur with excessive exposure to radiation, however the Lunar iDXA has technology that enables extremely precise and safe measurements. It uses a unique “K-edge filter” that absorbs X-rays to protect the patient against unnecessary exposure, resulting in a low radiation exposure of approximately 0.0003 mSv per scan. The exposure from one scan is equivalent to 17.6% of the average person’s daily exposure to radiation. For comparison, a normal chest X-Ray causes .010 mSv of radiation exposure per scan which is 588% of an individuals average daily exposure. There are no complications expected with the DXA procedure.

After preliminary tests, a 2-day run-in baseline energy balance diet low in BPA will occur (see Figure 2 above) in which 24-hour urine, fasting blood, muscle insulin sensitivity, hepatic glucose suppression and fecal microbiome will be assessed. Participants will then be randomized (blocked by sex and ethnicity) to either Diet+BPA or Diet+No BPA, in a double-blinded fashion. Similar to our previous intervention studies, the study statistician ([name]) will computer generate the randomization scheme but will not have contact with any participant. Repeated assessment of 24-hour urine collection of BPA for 3 consecutive days, and fasting blood, muscle insulin sensitivity, hepatic glucose suppression, and gut microbiome will occur at the end of the treatment period. Consumption of the final BPA or placebo will occur 1 hour prior to the muscle insulin sensitivity measurement and glucose stable isotope infusion.

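### As the text stands, a woman's baseline and end-of-treatment assessments cannot both fall 1 to 4 days after menstruation starts: the window allows a 3-day gap and the schedule needs 4 to 5

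*Combined protocol and SAP*

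**What the plan says.** The Participants section admits both sexes and sets one timing rule for women: "All testing in women will occur in the early follicular phase (1 to 4 days after start of menstruation) of the menstrual cycle". It exempts no assessment.

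The Overview describes a supervised stay "for 6 days (2-day baseline run-in, followed by 4-day treatment", and adds: "Main outcome measures (muscle insulin sensitivity and hepatic glucose suppression) will be assessed at baseline and treatment periods". Diet, Activity and Sleep Monitoring and Control repeats the length of stay: "for a total of 6 days (2-day baseline run-in followed by 4-day treatment". Potential risks to subjects describes the six days as consecutive, so the two assessments cannot be placed in different cycles.

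Sequence of Events says that "a 2-day run-in baseline energy balance diet low in BPA will occur (see Figure 2 above) in which 24-hour urine, fasting blood", the clamp measures and the fecal sample are obtained. Randomisation, blocked by sex and ethnicity, follows. The same measures are repeated when treatment ends, and the last dose is taken an hour before the second clamp.

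Aim 2 includes "inflammatory markers (adiponectin), and sex hormones (17-beta-estradiol), linked to the progression to type 2 diabetes" among its outcomes. The Outcome Measures section collects 17-beta-estradiol with the other fasting samples at both periods, so it has the same timing as the clamps.

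**The concern.** A window running from day 1 to day 4 is narrower than the time between the two assessments. If so, every woman who follows the schedule breaks the timing rule at one assessment or the other, and site staff have to decide which. Different choices for different women would put baseline and repeat on different cycle days across the sample.

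The outcome most exposed is 17-beta-estradiol, a named Aim 2 hormone. Its change from baseline in women would mix time on treatment with movement through the cycle. The clamp outcomes share the timing. The comparison of randomised groups is better protected, because both arms follow the same calendar and randomisation is blocked by sex.

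**Working it through.** **Inputs**
- Window: 1 to 4 days after onset (Participants).
- Stay: 2 run-in days, then 4 treatment days (Overview), consecutive (Potential risks to subjects).
- Baseline blood and clamp: within the run-in, so study day 1 or 2 (Sequence of Events).
- Repeat: end of treatment, an hour after the final dose, so study day 6 (Sequence of Events).

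**Reproducing the plan's own schedule**
- Stay: 2 + 4 = 6 days, with treatment on study days 3 to 6. BPA Dose and Duration agrees that treatment runs to day 6 ("one at baseline and three during treatment on days 4-6").
- Urine: the plan collects on 5 days in all, 3 of them consecutive treatment days. That leaves 5 − 3 = 2 baseline days, matching a 2-day run-in.

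**Gap allowed and gap needed**
- Allowed: 4 − 1 = 3 days.
- Needed: 6 − 2 = 4 days, or 6 − 1 = 5 days.

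**Trying every admission date**

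Let k be the number of days after onset on study day 1 (negative if admission comes before onset). Study day d then falls on day k + d − 1, and the repeat falls on day k + 5. For the repeat to be on days 1 to 4, k must lie between −4 and −1.

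| Baseline on study day | Baseline falls on day | k that puts baseline on days 1–4 | Repeat then falls on days | k that fits both |
|---|---|---|---|---|
| 1 | k | 1 to 4 | 6 to 9 | none |
| 2 | k + 1 | 0 to 3 | 5 to 8 | none |
| 3 (not in the text) | k + 2 | −1 to 2 | 4 to 7 | −1 only |

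With baseline inside the window, the repeat is 1 to 4 days late (baseline on study day 2) or 2 to 5 days late (study day 1).

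**Other ways to count the window**
- Calling the day of onset day 1 (0 to 3 days after onset) keeps the window four days wide. The number of admission dates that fit, for baseline on study day 1 / 2 / 3, is again 0 / 0 / 1.
- Adding the day of onset to the stated window (days 0 to 4) gives 0 / 1 / 2. The single fit for study day 2 is k = −1, with baseline on day 0 and repeat on day 4.

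**Margin in the single-fit cases (k = −1)**
- Baseline on study day 3, window 1–4: onset one day later than predicted puts baseline on day 0, outside. One day earlier puts the repeat on day 5, outside.
- Baseline on study day 2, window 0–4: one day later puts baseline on day −1, outside. One day earlier puts the repeat on day 5, outside.

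Every reading that fits requires admission before menstruation has started. The plan gives no method for predicting onset.

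**The case against.** The strongest reply is that the baseline clamp may really take place on the morning of study day 3, before the first dose. Sequence of Events refers to Figure 2 for the run-in, and that figure is missing from the reviewed copy.

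Several passages lean this way. Recruitment says: "During the treatment phase for 4 days participants will have a safety blood draw", and the student charge implies $30 / $7.50 = 4 draws. BPA Dose and Duration also counts four liver tests, "one at baseline and three during treatment on days 4-6". If these are the same four draws, the one called baseline is on study day 3. The plan also relies on the full two days of low-BPA diet to clear background exposure, and only a day-3 clamp follows all of it.

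This reading is plausible and limits how firmly the point can be put. But the draws are safety bloods, and the text places the clamp within the run-in. Even if the reading is right, only one admission date works, with no tolerance, so the plan would still need clarifying.

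The timing sentence might also be a loose scheduling rule, meant only for the start of testing. Read with full strictness it would cover screening tests and every urine day too. That is possible, but the wording covers all testing, and it gives staff no other rule to apply.

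Finally, the harm is limited: there is no bias between arms by this route, and the plan's stated goal is to compare the randomised groups. That stands, and it keeps the point below a threat to the main comparison.

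**Conclusion.** The concern holds on the text as written. The window permits 3 days between assessments and the schedule needs 4 or 5, so no admission date satisfies both. With baseline in the window, the repeat lands on days 5 to 8 or 6 to 9.

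This assumes that the baseline clamp is on study day 1 or 2, that the repeat is on study day 6, and that days are counted as calendar days. Figure 2 could change the first assumption, so confidence is medium. A day-3 baseline would turn an impossible rule into one that needs exact prediction of onset.

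The consequence is a stated control that cannot be met, no usable scheduling rule for women, and within-group change in women that is hard to interpret, chiefly for 17-beta-estradiol. It does not by itself bias BPA against placebo. The documents give no target number of women and no size for a cycle-day effect, so no number affected and no loss of precision is claimed. It should be corrected before women are scheduled.

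**What to change.** Reconcile Participants with Sequence of Events:

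1. Replace the timing sentence with a rule the 6-day stay can meet. Tie admission to a stated narrow range of days after an observed onset, and state the cycle day that results at each assessment. As arithmetic only: admission 1 to 3 days after onset, with baseline on study day 2, gives baseline on days 1 + 1 = 2 to 3 + 1 = 4 and repeat on days 1 + 5 = 6 to 3 + 5 = 8, without predicting onset. The repeat is then outside the present window, so the investigators must decide whether that range is acceptable.
2. If Figure 2 places the baseline clamp on study day 3, say so in Sequence of Events and state how onset will be predicted.
3. State which tests the rule covers, and record cycle day at both assessments.
4. For Hypothesis 3, where Statistical Analysis lists no covariates, specify that end-of-treatment estradiol is compared between groups adjusting for baseline estradiol and sex. This does not resolve the timing conflict, but it bases the estradiol result on the randomised comparison.

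The cost is protocol wording, one extra recorded field and one specified model using data already collected. The drawback is slightly tighter scheduling of women.

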The prevalence of diabetes is well established, affecting >29 million Americans, with 90-95% of these individuals diagnosed with type 2 diabetes.^{1,2} Although, diet, physical activity, obesity, and genetics play important roles in the etiology of type 2 diabetes, those established factors explain 30-60% of variance³; thus much still remains unknown. Emerging data suggests that synthetic non-persistent endocrine disruptors used in a variety of common consumer goods, including the mass industry-produced chemical bisphenol A (BPA), may play a pivotal role in type 2 diabetes rates.⁴⁻¹³ In support of this hypothesis, National Health and Nutrition Examination Survey (NHANES), Nurses' Health Study II (NHSII), and other cross-sectional data have shown associations between urinary BPA concentrations and type-2 diabetes^{14,15}, pre-diabetes¹⁶, insulin resistance¹⁷, and hemoglobin A1c.¹⁸ As a preliminary test, we conducted one of the only known studies at Cal Poly (IRB approved) in humans and found that consumption of a single, oral BPA dose of 50 µg/kg body weight immediately decreased glucose responses to an oral glucose tolerance test over 3 hours. These novel data were consistent with the one animal study in mice that showed that consumption of 10 µg/kg BW of BPA immediately (after 1 day) and significantly reduced glycemia. Interestingly, in longer mice studies, after 4 days of administration of 100 µg/kg BW of BPA, glycemia drastically increased and the mice became hyperinsulinemic.⁴ The primary purpose of this 2-group, randomized, double-blinded, experimental study is to determine whether oral consumption of BPA at a dose consistent with the US EPA reference safe dose,¹⁹ while controlling for energy intake and energy expenditure, has an independent effect on muscle insulin sensitivity and hepatic glucose suppression. Forty, normal-weight, sedentary adults will be randomly assigned to a 4-day energy balance diet plus oral BPA consumption at 50 µg/kg body weight (Diet+BPA) or 4-day energy balance diet plus oral placebo consumption (Diet+No BPA). The proposed experimental study will be the first to isolate the direct effects of BPA consumption on muscle insulin sensitivity and hepatic glucose suppression in humans, and will explore fecal microbiome species diversity and communities. The nature of this study is short-term (4 day exposure), and our and other previous preliminary studies showed that markers returned to normal after short-term BPA exposure.²⁰ Findings from this study will inform public health recommendations for food packaging, provide a framework for other studies in this area, and provide the first, much needed experimental evidence using gold standard measures as to whether BPA consumption over several days poses any risk of type 2 diabetes.

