diabetes risk markers.²¹ After an overnight fast, eleven, healthy college students (8W, 3M; 40% Hispanic, 21.0 ± 0.8 yrs.; 24.2 ± 3.9 kg/m²) were randomized in a balanced, double-blinded, cross-over fashion to oral consumption of Placebo (PL), BPA at 4 μ g/kg BW (BPA 4), and BPA at 50 μ g/kg BW (BPA 50). Blood BPA, glucose, insulin, and C-Peptide were assessed at baseline, minutes 15, 30, 45, 60, and then every 30 minutes for the next 2 hours in response to a 75g oral glucose tolerance test using a linear mixed model (See Figure). BPA concentrations in the BPA 50 condition compared to both PL and BPA 4 was higher at minutes 30 through 180 ($P<0.05$), and BPA 4 was significantly higher than PL at the same time points ($P<0.05$). **Participants reported no gastrointestinal distress or changes in subjective appetite rating with the varying doses of BPA.** We also investigated effects on diabetes biomarkers. While group x time interactions did not reach significance, significant (or near) main effects for condition were observed for lower glucose (Tukey-adjusted $P=0.036$; Figure 1A), lower insulin (Tukey adjusted $P=0.05$; Figure 1B) and C -Peptide concentrations (Tukey adjusted $P = 0.003$; Figure 1C) in the BPA 50 vs BPA PL or BPA 4 conditions. These data are consistent with animal data⁴ suggesting that oral BPA consumption had an immediate impact to *lower* blood glucose, and may potentially alter insulin sensitivity and/or hepatic glucose suppression, both of which will be assessed in the current proposal.

Intervention studies to reduce BPA exposure. The PI ([name]), and Co-I's ([name] and [name]) have conducted two, novel 3-week intervention studies to reduce BPA exposure in women with normal-weight and obesity, respectively. Results indicate that from study entry to 3-weeks in women with normal-weight, the intervention significantly decreased geometric mean creatinine-adjusted urinary BPA by -0.71 ng/m (-50%) whereas women in the control significantly increased urinary BPA by 0.32 ng/mL (+66%; $P=0.04$).²² We then adapted the 3-week intervention to women with obesity ([name] et al, *BMC Women's Health*, In review February 2018). From study entry to

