(BPA <0.20 ng/g fresh weight; e.g. organic, whole foods, etc.). In our laboratory we have pretested foods from local grocery stores in San Luis Obispo, CA that are low in BPA (<0.20 ng/g fresh weight) using a commercially available kit (Detroit R&D, Inc., Detroit MI), to be used during the feeding portion of the proposed study. The composition of the diet will be approximately 55% carbohydrate, 30% fat, and 15% protein, consisting of all natural, organic foods, and all food will be prepared and stored in BPA-free containers, glass containers, etc. The 2-day baseline “fresh food” diet low in BPA is sufficient to reduce background BPA exposure.²⁸ [name] (Co-I and Registered Dietician), will aid the [name] in estimating calorie needs and in preparing all meals and macronutrient composition for both groups. During the treatment phase, both groups will have similar diets with the only difference in BPA or placebo consumption. Oral BPA and placebo consumption will be administered on a vanilla wafer cookie, similar to our preliminary study and other previous pharmacokinetic studies.^{36,38} A single dosing solution (10 mg/ml) for BPA will be prepared by dissolving d6-BPA (C/D/N Isotopes, Pointe-Claire, Quebec) in absolute 95% ethanol (Acros Organics, Janssen Pharmaceutical, Belgium). For placebo, d6-BPA will not be included in the ethanol solution. A research assistant not involved in any other aspect of this study will make the dosing solutions. Approximately 1 ml aliquots will be passed twice through a sterile micro filter to aid in removal of bacteria and placed onto a vanilla wafer cookie (20 grams), allowing the ethanol to dry six hours before daily consumption. The vanilla wafer cookies with BPA and placebo look, weigh, and taste identical.

Sequence of Events

Participants will complete a demographic questionnaire assessing age, race, ethnicity, and weight history, as previously used in our studies.^{30,41} Participants will also complete a health and fitness history questionnaire. Both of these questionnaires ask personal questions including the use of illegal substances as well as confidential mental and physical health information. This information will be collected using RedCap, an encrypted data storage

Figure 2. Overview of experimental study design. Participants will reside in our laboratory facilities during which energy intake, energy expenditure and sleep will be monitored and controlled.

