program. Any paper copies of participant's answers will be stored in a locked filing cabinet and destroyed after 7 years. Only trained study staff who have undergone significant training on confidentiality and privacy, HIPAA regulations and patient safety will collect these completed questionnaires and have access to the results for research purposes only. No research volunteers including students will administer these questionnaires or have access to the questionnaires. Height will be measured by stadiometer (Ellard Instrumentation LTD., Monroe, WA) and weight by balance scale (Continental Scale Corporation, Bridgeview, IL), and BMI (kg/m^2) will be calculated. Resting metabolic rate (RMR) will be measured in the morning after an overnight fast using a ventilated hood and indirect calorimetry to estimate energy requirements consistent with best practice methods⁴². After a 60-minute period of relaxation, subjects will sit comfortably in a reclining chair for up to 60 minutes while expired air is collected using the metabolic measurement system (Parvomedics TrueMax 2400, Sandy, UT). Kien and Ugrasbul⁴³ reported that energy requirements estimated from RMR and the appropriate activity factor were strongly correlated ($r = 0.73$) with energy requirements measured during 28-days of controlled feeding. Also, participants will complete a 3-day (2 weekdays, 1 weekend day) dietary recall using the automated NCI ASA-24 (<https://epi.grants.cancer.gov/asa24/>). Thus, total energy requirements will be estimated using RMR and the appropriate activity factor and 24 h dietary recalls, as others and we previously described^{29,32,41,43}. Body composition will be measured as a preliminary test using a Lunar iDXA scan (General Electric Healthcare Company, USA), the new gold standard for assessing body composition. It will require the

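### The written cookie preparation (about 1 ml of a 10 mg/ml solution) delivers 10 mg of BPA, which matches the assigned 50 µg/kg only at a body weight of 200 kg

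*Combined protocol and SAP*

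**What the plan says.** **Assigned dose.** The opening summary has forty adults "randomly assigned to a 4-day energy balance diet plus oral BPA consumption at 50" µg/kg body weight, or to the same diet with placebo. The Overview under Methods repeats this. BPA Dose and Duration gives the rationale: "The dose of BPA selected in the proposed study is consistent with the US EPA reference dose of" 50 µg/kg.

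**Preparation.** Diet, Activity and Sleep Monitoring and Control states: "A single dosing solution (10 mg/ml) for BPA will be prepared by dissolving d6-BPA" in ethanol. Then: "Approximately 1 ml aliquots will be passed twice through a sterile micro filter to aid in removal of bacteria and placed onto a vanilla wafer" (each weighs 20 g). The ethanol dries for six hours and the cookie is eaten daily. Placebo is the same ethanol without d6-BPA. The solutions are made by an assistant who has no other role in the study.

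**Body size.** Participants are "normal-weight (BMI = 18.5 to 24.9" kg/m². Sequence of Events records "weight by balance scale", but does not link that weight to dose preparation.

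**Earlier use.** In the preliminary study, participants "were randomized in a balanced, double-blinded, cross-over fashion to oral consumption of Placebo (PL), BPA at 4" or 50 µg/kg, so that study dosed per kilogram.

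**Safety reference points.** The plan cites a no-observed-adverse-effect level (NOAEL) of 5 mg/kg per day and pharmacokinetic studies at 50 to 100 µg/kg. It also reports that "typical BPA exposures range from 0.43 to 1.5" µg/kg.

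**The concern.** A per-kilogram dose needs a step that turns weight into an amount. The plan gives one concentration and one approximate volume for everyone, and the product of the two is far from the assigned dose for anyone who could be enrolled. If the full 1 ml goes on the cookie, two things follow.

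- **Safety.** The low-risk rating rests on 50 µg/kg being the reference dose. The tolerability evidence comes from the preliminary study (4 and 50 µg/kg) and from single-dose work at 50 to 100 µg/kg. Potential Risks to Subjects says the effect of repeated dosing on liver and kidney enzymes is unknown. Most participants would be above the cited range for four days.
- **Interpretation.** The stated purpose is to test the effect at the reference dose. A fixed 10 mg makes the per-kilogram dose fall as weight rises, so the BPA arm would receive neither the reference dose nor a uniform one. The last dose is taken one hour before the clamp, about when blood BPA is said to peak, so a dose error would coincide with the main outcome measurement.

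**Working it through.** **Inputs from the plan:** concentration 10 mg/ml; volume about 1 ml; dose 50 µg/kg = 0.05 mg/kg; BMI 18.5 to 24.9 kg/m²; NOAEL 5 mg/kg = 5,000 µg/kg per day.

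**Assumptions:** heights of 1.50 to 1.90 m, because the plan gives no heights or weights; 0.8 to 1.2 ml as a range for an approximate 1 ml.

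**Step 1: try to reproduce 50 µg/kg.** Amount = concentration × volume = 10 mg/ml × 1 ml = 10 mg. Matching weight = 10 / 0.05 = 200 kg. At BMI 24.9 the height is √(200 / 24.9) = 2.83 m. With 0.8 to 1.2 ml the matching weight is 8 / 0.05 = 160 kg to 12 / 0.05 = 240 kg. The stated dose is not reproduced, and this result does not need the height assumption.

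**Step 2: size of the excess.** Lightest: 18.5 × 1.50² = 41.6 kg. Heaviest: 24.9 × 1.90² = 89.9 kg. Dose at 1 ml = 10,000 µg / weight. Volume needed = 0.05 × weight / 10.

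| Weight (kg) | Volume needed at 10 mg/ml (ml) | Concentration needed for 1 ml (mg/ml) | Dose if 1 ml is used (µg/kg) | Multiple of 50 µg/kg |
|---|---|---|---|---|
| 41.6 | 0.21 | 2.1 | 240 | 4.8 |
| 50 | 0.25 | 2.5 | 200 | 4.0 |
| 70 | 0.35 | 3.5 | 143 | 2.9 |
| 80 | 0.40 | 4.0 | 125 | 2.5 |
| 89.9 | 0.45 | 4.5 | 111 | 2.2 |

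**Step 3: sensitivity to volume.** Lowest: 8,000 / 89.9 = 89 µg/kg (1.8 times). Highest: 12,000 / 41.6 = 288 µg/kg (5.8 times). The dose exceeds 50 µg/kg throughout. It does not exceed 100 µg/kg throughout: at 1 ml it does so below 100 kg (2.00 m at BMI 24.9), but at 0.8 ml only below 80 kg (1.79 m at BMI 24.9).

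**Step 4: could filtration losses explain it?** To bring 1 ml down to 50 µg/kg, the loss would have to be 1 − 50/111 = 55% for the heaviest and 1 − 50/240 = 79% for the lightest. The plan describes no such loss.

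**Step 5: margin to the NOAEL.** At 1 ml: 5,000 / 240 = 21-fold to 5,000 / 111 = 45-fold. Over 0.8 to 1.2 ml: 5,000 / 288 = 17-fold to 5,000 / 89 = 56-fold.

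**Separate wording check.** One sentence under Bisphenol A Consumption places the dose inside the usual US exposure range; a later one in the same section places it above. Against 0.43 to 1.5 µg/kg, the dose is 50 / 1.5 = 33 to 50 / 0.43 = 116 times typical, so the first sentence is wrong.

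**The case against.** The assigned dose is unambiguous, and a per-kilogram dose implies scaling. Weight is measured, the preliminary study dosed per kilogram, and the cookie method is said to follow that study and earlier pharmacokinetic work, where a dispensing step may be described. The paragraph on the cookies is a narrative, not a dispensing worksheet. The 1 ml could be the portion that is filtered, with a weight-based volume then drawn from it. Delivered dose can also be checked. Urine is collected over 24 hours on several days with volumes measured, and the plan cites 92% recovery in 24 hours. At 70 kg, 10 mg against 3.5 mg would mean about 9.2 against 3.2 mg excreted. A physician reviews daily chemistry and blood counts and can stop treatment. The comparison of BPA with placebo would remain randomized at whatever dose was given.

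Much of this stands. Scaling by weight is the likely intention, an overdose is not demonstrated, and the NOAEL margin and monitoring limit the harm. It does not remove the inconsistency. The sentence puts the filtered aliquots themselves on the cookie, and no later dispensing step appears. One common solution points away from individual concentrations. The cited methods cannot be consulted from this document. The urine samples are frozen for later assay, so they could reveal a wrong dose but not prevent one. Because the solutions are made by someone outside the rest of the study, the written instruction has to be sufficient.

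**Conclusion.** The point holds and should be corrected before dosing. The only volume and concentration in the plan yield 10 mg, which is wrong for every eligible participant: 50 µg/kg would require 200 kg. Under the assumed heights, the literal dose is 2.2 to 4.8 times the stated one at 1 ml, and 1.8 to 5.8 times at 0.8 to 1.2 ml. That the stated dose is exceeded does not depend on those assumptions in any realistic way; how far it is exceeded does, as does whether an individual passes 100 µg/kg.

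This is an inconsistency in the written plan, not evidence of what participants received. The solution is usable for the assigned dose if about 0.21 to 0.45 ml is dispensed; what is missing is the instruction to do so. The sentence calling the dose typical is a minor, separate error, and the conclusion does not rest on it.

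**What to change.** State one rule in the preparation paragraph. Either:

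- volume on the cookie (ml) = 50 µg/kg × weight (kg) / 10,000 µg/ml, that is 0.005 ml per kg; or
- keep 1 ml and prepare each participant's solution at 0.05 mg/ml per kg of body weight (3.5 mg/ml at 70 kg).

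Name the weight measurement to be used. Apply the same volume rule to placebo so that preparation does not reveal allocation. Record the mg and µg/kg given to each participant each day. If a different amount was intended, correct the stated dose and the safety text instead. Separately, delete the sentence under Bisphenol A Consumption that describes the dose as within typical exposure.

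The cost is a wording amendment and one line on the dosing worksheet, with no added participants or procedures.
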